11.8.2 Hypoglycemic Treatment Emergent Adverse Events

Hypoglycemic AEs which are only documented on the AE page and for whom the Hypoglycemia page is blank or missing will not be considered in the analyses which are described below.

On the Hypoglycemia page further details are documented if the answer to the question "Is this a hypoglycemic event?" on the Adverse Event page is 'Yes'. Hypoglycemic TEAEs will be reported using data recorded on both the Adverse Event page and the Hypoglycemia page as follows:

- Severe Hypoglycemic event (Table 6, Analysis 6)
- Symptomatic Hypoglycemic event (Table 6, Analysis 9)

nutrition disorders				"Was third party intervention required for this episode of hypoglycemia?" is Yes
---------------------	--	--	--	--

Additionally, summary of ADA graded hypoglycemic event and TEAE by ERIPD subgroup will be produced for per protocol analysis set 2 and 3 (Table 6, Analysis 12).

11.8.3 Deaths and Serious Adverse Events

SAEs, IP-related SAEs, serious hypoglycemic (Table 6, Analysis 7), and IP-related Serious hypoglycemic events will be summarized separately by preferred term for the SS (Table 6, Analysis 8). All SAEs recorded on the CRF will be listed for subjects in the SS.

A table presenting the number and percentage of subjects by preferred term who experienced fatal TEAEs during the study will be presented for the SS. A further summary of Serious treatment-emergent SAEs by preferred term will be provided. Deaths occurring in the study will also be listed for all subjects in the SS.

11.8.4 Laboratory Data

Laboratory test results will be reported in International System of Units (SI) units. For observed values below the lower limit of quantification/detection (for example total bilirubin reported as <3 µmol/L), the lower limit (3 µmol/L) will be used as the imputed value.

Laboratory values and change from baseline will be summarized using descriptive statistics by time point and treatment group. Hematology, chemistry, thyroid-stimulating hormone (TSH) and free thyroxine (T4) results will be collected during screening, at visit Week 12 and visit Week 26.

Shift tables of the maximum post-baseline value will be presented by treatment group, reference range and time point. Shift tables will include all laboratory assessments. In addition, subject listings of abnormal (grade ≥ 3) post-baseline laboratory toxicities will be provided. Standard ranges from the central laboratory will be used for the laboratory analysis.

Lab assessments will be grouped for summary as follows:

- Hematology – white blood cell (WBC) parameters: WBC count and differentials
- Hematology – red blood cell (RBC) parameters: hemoglobin, hematocrit, RBC count, mean corpuscular hemoglobin, mean corpuscular hemoglobin concentration, mean corpuscular volume
- Hematology – other parameters: platelets
- Serum chemistry – hepatobiliary parameters: alanine aminotransferase (ALT), aspartate aminotransferase (AST), total bilirubin, alkaline phosphatase
- Serum chemistry – general chemistry: sodium, potassium, chloride, bicarbonate, total protein, calcium, creatine kinase, total cholesterol, high-density lipoprotein, low-density lipoprotein, triglycerides
- Serum chemistry – renal function tests: urea, creatinine
- Thyroid – T4, TSH

A summary assessing the potential hepatotoxicity and potential Hy's Law will be presented. A listing of these potentially hepatotoxic values (along with the corresponding amount times upper limit normal) will be presented.

Post-baseline potentially clinically significant (PCS) vital signs results will be summarized and will include the following categories:

- Pulse < 50 beats per minute
- Pulse > 120 beats per minute
- Pulse \geq 30 beats per minute increase from baseline
- Pulse \geq 30 beats per minute decrease from baseline
- Systolic blood pressure > 150 mmHg or diastolic blood pressure > 100 mmHg
- Systolic blood pressure > 200 mmHg or diastolic blood pressure > 110 mmHg
- Weight \geq 5% increase from baseline
- Weight \geq 5% decrease from baseline

A listing of the observations with PCS vital sign results will be provided.

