### 8.7.3.2 Safety

- The incidence and severity of all treatment-emergent adverse events and the following subgroups:
  - Hypoglycemia, which will be fully documented prospectively in the Hypoglycemic Events Record
  - Serious adverse events, including fatal events
  - Adverse events leading to termination of the study treatment and/or early withdrawal from the study
  - IP-related adverse events
  - Injection site reactions
- The incidence of clinically significant laboratory abnormalities
- The incidence of clinically significant abnormalities in ECG and vital signs

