### **11.5.1 Abnormal Laboratory Test Results**

Changes or abnormalities in clinical laboratory results judged to be clinically significant by the Investigator will be recorded as adverse events. If an unexplained abnormal laboratory test result occurs, the Investigator or designee will promptly repeat the test and monitor the subject until the result has returned to the normal range or an adequate explanation of the abnormality is found.

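### Laboratory shift tables built on the maximum post-baseline value can show a transient low as normal, for parameters where low is an abnormal direction

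*SAP*

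**What the plan says.** SAP Section 11.8.4 sets the rule in one sentence: "Shift tables of the maximum post-baseline value will be presented by treatment group, reference range and time point". The next sentence gives its scope: "Shift tables will include all laboratory assessments". No minimum or worst-direction value is named there.

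The parameter groups in the same section include "red blood cell (RBC) parameters: hemoglobin, hematocrit, RBC count", a white-cell group with differentials, "other parameters: platelets", and "general chemistry: sodium, potassium, chloride, bicarbonate, total protein, calcium, creatine kinase". On timing, hematology, chemistry and thyroid "results will be collected during screening, at visit Week 12 and visit Week 26", which gives two scheduled post-baseline samples per subject.

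Protocol Section 8.7.3.2 lists as a secondary safety endpoint "The incidence of clinically significant laboratory abnormalities". Under Protocol Section 11.5.1, after an unexplained abnormal result "the Investigator or designee will promptly repeat the test and monitor the subject until the result has returned to the normal range", or until the abnormality is adequately explained.

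**The concern.** A maximum suits parameters that matter when they rise, such as ALT, AST and bilirubin. For red cells, white cells, platelets and electrolytes, a fall is also abnormal and is often the change of interest. A maximum-based shift table favors the higher reading every time, so it captures all highs and drops any low that is accompanied by a normal value.

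Elsewhere the SAP looks both ways. The pulse and weight categories cover increases and decreases. The ECG heart-rate categories in Section 11.8.6 have a lower and an upper cut-off. The thyroid abnormality definition is any TSH or free T4 result outside the normal range. Appendix 2 grades low calcium, potassium and sodium. The one-directional shift rule therefore looks like an oversight.

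At stake is a planned between-arm display of laboratory abnormalities that does not depend on an investigator's judgment, in an open-label trial. The primary and key secondary analyses are not touched.

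**Working it through.** The plan gives no figure to reproduce. The check is one of logic, followed by an illustration of size.

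**Step 1: what a maximum can show.** Let L and U be the lower and upper limits of normal, and x1, ..., xk the values that enter one table cell for a subject.

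- max(x) > U if and only if at least one value is above U, so every high is captured.
- max(x) < L if and only if all k values are below L, so one normal value removes the low.

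**Step 2: the two readings of the sentence.** The sentence speaks both of a post-baseline maximum and of time point, so the maximum could be taken across visits or within each visit. The table below shows what each reading gives for a subject who is normal at baseline.

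| Post-baseline values | Maximum across visits | Maximum within visit | Minimum |
|---|---|---|---|
| Week 12 low, Week 26 normal, no repeat | Normal | Low at Week 12 | Low |
| Week 12 low, normal repeat assigned to Week 12, Week 26 normal | Normal | Normal at both | Low |
| Low at Weeks 12 and 26, no normal repeat | Low | Low at both | Low |

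The second row matters because Protocol Section 11.5.1 calls for repeats of unexplained abnormal results. The text available for this review does not show whether an unscheduled repeat is assigned to the scheduled visit, because the visit-window definitions in SAP Section 7.1 are not included.

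**Step 3: size under the across-visit reading.** The documents give no rates of low values, so p and r below are assumptions. Inputs:

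- two post-baseline samples per subject (SAP Section 11.8.4);
- 275 subjects per arm (SAP Section 5.1), all assumed to have both samples;
- probability p of a low value at each visit;
- bivariate normal values with correlation r between visits.

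Formulas:

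- P(shown as low) = P(low at both visits)
- P(any low) = 2p − P(low at both visits)
- Share not shown = 1 − P(low at both visits) / P(any low)

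| p | r | P(both low) | P(any low) | Share not shown | Per 275: any low | Per 275: shown as low |
|---|---|---|---|---|---|---|
| 2% | 0.5 | 0.0034 | 0.0366 | 91% | 10.1 | 0.9 |
| 2% | 0.8 | 0.0085 | 0.0315 | 73% | 8.7 | 2.3 |
| 5% | 0.5 | 0.0122 | 0.0878 | 86% | 24.1 | 3.4 |
| 5% | 0.8 | 0.0248 | 0.0752 | 67% | 20.7 | 6.8 |
| 10% | 0.5 | 0.0324 | 0.1676 | 81% | 46.1 | 8.9 |
| 10% | 0.8 | 0.0562 | 0.1438 | 61% | 39.5 | 15.5 |

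For p = 5% and r = 0.5: P(any low) = 2 × 0.05 − 0.0122 = 0.0878, and the share not shown is 1 − 0.0122 / 0.0878 = 0.86. With r = 0 the share would be 97%, but independence between one subject's own hemoglobin or platelet values is not realistic, so that figure is not used. A subject with only one post-baseline value cannot be misclassified this way.

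**Step 4: size under the within-visit reading.** A low is lost only where a non-low repeat is counted in the same visit. The documents give no frequency for this, so no figure is attached.

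**The case against.** The strongest reply is that the sentence itself says the tables are presented by time point. On that reading a low Week 12 value appears in the Week 12 table, and the percentages above do not apply. This stands as a limit on size: the wording supports either reading, and the within-visit loss is confined to visits with repeats. It does not clear the rule, because a maximum within a visit still prefers a normal repeat to the low value that prompted it, if that repeat is assigned to the visit.

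Other planned outputs also carry part of the load:

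- SAP Section 11.8.4 lists post-baseline toxicities of Grade 3 or higher by subject.
- Protocol Section 11.5.1 has results judged clinically significant recorded as adverse events, so they reach the adverse event tables whatever a later value shows.
- Protocol Section 12.6 includes the minimum and the 25th percentile in the descriptive statistics, and SAP Section 11.8.4 gives such statistics by visit and arm.
- SAP Table 6 cites a Section 11.8.4.1 with a graded fasting glucose table. That section is not in the text available here and the table shells are a separate document, so further low-direction displays cannot be ruled out.

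All of this stands and narrows the point. What these outputs do not supply, as far as the text shows, is a count by arm of subjects who shift from normal to a Grade 1-2 low.

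A reader might go further and infer that the arms will look alike on low blood counts and electrolytes whatever the drug does, or that the safety endpoint depends on these tables alone. The documents do not support that. A subject low at every assessment is still shown as low, so a sustained effect would appear. The endpoint concerns clinically significant abnormalities, which have their own route through adverse event reporting.

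**Conclusion.** The point holds, with a bounded effect. As written, SAP Section 11.8.4 can tabulate a transient low as normal in any parameter where low is an abnormal direction.

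Across visits, only subjects low at every post-baseline assessment appear as low. For an assumed 5% low rate per visit and correlation of 0.5 to 0.8, about 86% to 67% of subjects with any low value are not shown as low. Over assumed rates of 2% to 10% and the same correlations, the range is 91% to 61%. Within visits, the loss is limited to visits with repeat tests assigned to them. The rates and correlations are assumptions, so these figures illustrate the size and do not predict it.

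The damage is confined to the descriptive shift tables and falls mainly on Grade 1-2 lows. No hypothesis test is affected. The correction is worth making because it is specific and nearly free.

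**What to change.** In SAP Section 11.8.4:

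- present shifts to low using the minimum post-baseline value and shifts to high using the maximum, both including unscheduled and repeat results;
- keep the maximum alone only for parameters with a single, high abnormal direction (e.g., ALT, AST, bilirubin);
- state whether time point means one table per visit or one overall post-baseline table and, if per visit, how repeats are assigned.

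The cost is a short change to the SAP text and a minimum-value version of tables already planned. No new data are needed.

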11.8.6 Electrocardiograms

Values and change from baseline in ECG results will be summarized by time point and treatment group. Descriptive statistics will be shown for baseline and visit Week 26. Post-baseline PCS ECG results will be summarized and will include the following categories:

- Heart rate < 50 beats per minute
- Heart rate > 100 beats per minute
- PR Interval \geq 200 msec
- QRS Interval \geq 120 msec
- QT Interval \geq 450 msec
- QT Interval change from baseline \geq 30 msec - < 60 msec
- QT Interval change from baseline \geq 60 msec
- Corrected QT using Fridericia's formula (QTcF) Interval \geq 450 - < 480 msec
- QTcF Interval \geq 480 - < 500 msec
- QTcF Interval \geq 500 msec
- Corrected QT using Bazett's formula (QTcB) Interval \geq 450 - < 480 msec
- QTcB Interval \geq 480 - < 500 msec
- QTcB Interval \geq 500 msec

where QTcF = QT/[(heart rate/60)^(1/3)] and QTcB = QT/[(heart rate/60)^(1/2)].

A listing of the observations with PCS ECG results will be provided.

12. Validation

PRA's goal is to ensure that each TFL delivery is submitted to the highest level of quality. Our quality control procedures will be documented separately in the study specific quality control plan.

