### 10.4 Electrocardiogram

Computerized 12-lead ECG recordings will be obtained, after the subject has been supine for 5 minutes. Each lead will be recorded for at least 3-5 beats at a speed of 25 mm/sec paper speed and 10 mm/mV amplitude. At a minimum, heart rate, P, PR, QRS, QT and corrected

QT intervals (msec) will be recorded from the 12-lead ECG. A copy of all ECGs will be retained on site and these may be collected for central review if required (i.e., in case emerging ECG data necessitate expert evaluation).

For the purposes of screening, the Investigator or a designee will evaluate whether the ECG is normal or abnormal, and if abnormal, whether the abnormality will exclude the subject from participating in the study.

Investigators may repeat ECGs for quality or safety reasons. Any abnormal finding deemed to be clinically relevant by the Investigator will be reported as an adverse event. Subjects with clinically relevant cardiovascular side effects or adverse events, or clinically relevant ECG changes must be withdrawn from the study (see [Section 8.4.3](#)).

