### **11.5.2 Abnormal Physical Examination Findings or ECG Changes**

Changes or abnormalities in physical examination findings or ECGs judged to be clinically significant by the Investigator will be recorded as adverse events.

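### SAP 11.8.6 prints the Fridericia and Bazett corrections inverted, so QTc derived as printed is too low above 60 bpm and too high below it

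*SAP*

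**What the plan says.** SAP 11.8.6 (Electrocardiograms) summarises ECG values and changes from baseline, and tabulates post-baseline potentially clinically significant (PCS) results. Two sets of QTc categories are named by method, "Corrected QT using Fridericia's formula (QTcF) Interval" and "Corrected QT using Bazett's formula (QTcB) Interval", each with bands of 450 to <480, 480 to <500, and 500 msec or more. The same list has categories for heart rate, PR, QRS, uncorrected QT of 450 msec or more, and change in QT from baseline. Heart rate is in beats per minute, as in "Heart rate > 100 beats per minute".

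After the list the section defines the two corrected intervals: "where QTcF = QT/[(heart rate/60)^(1/3)] and QTcB = QT/[(heart rate/60)^(1/2", with the final brackets cut here. It then adds: "A listing of the observations with PCS ECG results will be provided".

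Protocol 10.4 names heart rate, QT and corrected QT among the items for which "QT intervals (msec) will be recorded from the 12-lead ECG". It does not name the correction behind that recorded value.

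**The concern.** Fridericia's correction divides QT by the cube root of RR, and Bazett's by the square root of RR, with RR in seconds. With heart rate in beats per minute, RR = 60/heart rate. The printed formulas divide by powers of heart rate/60, which is 1/RR. They therefore multiply by the factor they should divide by. QT shortens as heart rate rises, and the printed versions add to that dependence where a correction should remove it.

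At stake is the descriptive QTc safety output: the QTcF and QTcB values and changes from baseline, the six bands, and the QTc entries in the PCS listing. The SAP's Appendix 2 is titled as covering CTCAE grading of QTc as well as laboratory values, so any grade taken from a derived QTc would carry the same error. Clinically significant ECG abnormalities are a listed secondary safety endpoint in both documents (Protocol 8.7.3.2, SAP 6.3.2).

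**Working it through.** The plan states no numerical result to reproduce here, so the check compares the printed formulas with the methods they name.

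**Inputs.** The printed formulas, the 450/480/500 msec bands, the uncorrected QT category and the heart rate unit all come from SAP 11.8.6. The definitions of the two named methods use RR = 60/HR. The HR and QT pairs below are assumptions for illustration. They stay within 50 to 100 bpm, the range that the SAP's own heart rate categories (<50 and >100) leave unflagged.

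**Formulas**, with k = 1/3 for QTcF and k = 1/2 for QTcB:

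- standard = QT/(60/HR)^k
- printed = QT/(HR/60)^k
- printed/standard = (60/HR)^(2k), that is (60/HR)^(2/3) for QTcF and 60/HR for QTcB

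**Ratio, and the raw QT (msec) at which each version reaches 450 msec:**

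| HR | Ratio QTcF | Ratio QTcB | QTcF: standard / printed | QTcB: standard / printed |
|---|---|---|---|---|
| 50 | 1.129 | 1.200 | 478.2 / 423.5 | 493.0 / 410.8 |
| 55 | 1.060 | 1.091 | 463.2 / 437.1 | 470.0 / 430.8 |
| 60 | 1.000 | 1.000 | 450.0 / 450.0 | 450.0 / 450.0 |
| 75 | 0.862 | 0.800 | 417.7 / 484.7 | 402.5 / 503.1 |
| 90 | 0.763 | 0.667 | 393.1 / 515.1 | 367.4 / 551.1 |
| 100 | 0.711 | 0.600 | 379.5 / 533.5 | 348.6 / 580.9 |

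For example, at 75 bpm QTcF reaches 450 at 450 × (60/75)^(1/3) = 417.7 msec by the standard formula, and at 450 × (75/60)^(1/3) = 484.7 msec as printed.

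**Missed prolongation above 60 bpm.** The uncorrected category takes over at QT 450, so the gap runs from the standard threshold up to QT 449 (whole msec):

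- 75 bpm: QT 418–449 (standard QTcF 450–484) falls in neither a printed QTcF band nor QT ≥450. For QTcB the gap is QT 403–449 (standard 451–502).
- 100 bpm: the gaps are QT 380–449 (standard QTcF 450–532) and QT 349–449 (standard QTcB 451–580).

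**False flags below 60 bpm.** At 55 bpm, QT 438–463 has a standard QTcF of 425–449.8 but is placed at 450 or above.

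**Single cases (msec):**

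| HR | QT | QTcF: standard / printed | QTcB: standard / printed |
|---|---|---|---|
| 90 | 440 | 503.7 / 384.4 | 538.9 / 359.3 |
| 100 | 400 | 474.3 / 337.4 | 516.4 / 309.8 |
| 50 | 440 | 414.1 / 467.6 | 401.7 / 482.0 |
| 70 | 380 | 400 / 361 | 410 / 352 |

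In the last row the values are wrong but no category changes.

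**Internal check.** Above 60 bpm the printed QTc is always smaller than QT. Any ECG that reaches a printed QTc band therefore already has QT ≥450. At those heart rates the QTc bands identify no one whom the uncorrected category has not already found, which defeats their purpose.

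**The case against.** The strongest reply is that this may be an error of text only. The intended methods are named, a programmer may have used the standard formulas or the corrected QT recorded under Protocol 10.4, and SAP Section 12 refers to a separate quality control plan. That is possible, and it is why the consequence is stated conditionally. But the definition follows directly on the QTcF and QTcB bands and reads as the rule for the tabulated values. It is also the only derivation in the text available. Parts of the public SAP are missing, so a statement on the QTc source elsewhere cannot be excluded.

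Other points limit the reach, and they stand:

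- The ECG output is descriptive. Protocol Table 1 schedules ECGs only at screening and Week 26.
- The same formula applies to both arms. Nothing in the documents suggests that heart rate differs by arm, so no directional bias in the comparison is shown.
- New prolongation may still reach the PCS table through the QT change-from-baseline categories (≥30 to <60 and ≥60 msec).
- No passage uses the QTc bands for eligibility, withdrawal or monitoring. Those rest on the investigator, and changes in "ECGs judged to be clinically significant by the Investigator will be recorded as adverse events" whatever the formula gives.

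None of this makes the printed formulas correct, and none of it repairs the QTc tables if they were built from them.

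**Conclusion.** The point holds. Both formulas are inverted and agree with the named methods only at 60 bpm. The same inversion appears in both, in plain text, so a PDF-reading fault is unlikely. If followed, QTcF and QTcB are off by +13%/+20% at 50 bpm, −14%/−20% at 75 bpm and −24%/−33% at 90 bpm. A category changes only when a threshold is crossed, and a very long QT is still flagged. The number of subjects affected is unknown, because the HR and QT pairs are assumed and the documents hold no ECG data. The heart rate, PR, QRS and uncorrected QT categories, the investigator-reported ECG adverse events, and the antibody and HbA1c analyses are not affected. This should be fixed, but no inferential conclusion of the trial rests on it.

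**What to change.** In SAP 11.8.6, print QTcF = QT/[(60/heart rate)^(1/3)] and QTcB = QT/[(60/heart rate)^(1/2)]. It would also help to add a sentence saying whether the tables and PCS listing use these derived values or the corrected QT recorded under Protocol 10.4; the formula correction does not depend on that sentence. Check the analysis-dataset specification and the derivation program against the corrected line, including any QTc grading under Appendix 2.

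The cost is one corrected line, one sentence and a program check. The ECG tables and listing need re-running only if the program followed the printed formulas. No new data are needed.

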Appendix 1 Glossary of Abbreviations

Glossary of Abbreviations:

ADA	American Diabetes Association
ADaM	Analysis Data Model
AE	Adverse Event
AIA	Anti-Insulin Antibodies
ALT	Alanine Aminotransferase
ANCOVA	Analysis of Covariance
AST	Aspartate Aminotransferase
ATC	Anatomical Therapeutic Classification
BID	Twice Daily
BMI	Body Mass Index
CDISC	Clinical Data Interchange Standard Consortium
CGM	Continuous Glucose Monitor
CI	Confidence Interval
CRF	Case Report Form
CTCAE	Common Terminology Criteria for Adverse Event
CTMS	Clinical Trial Management System
CV	Coefficient of Variation
ECG	Electrocardiogram
EIIPD	Efficacy-Interfering Important Protocol Deviation
EMA	European Medicines Agency
ERIPD	Eligibility-Related Important Protocol Deviation
EOT	End of Treatment
FAS	Full Analysis Set
FBG	Fasting Blood Glucose
FDA	Food and Drug Administration
HbA1c	Glycosylated Hemoglobin
Hgb	Hemoglobin
ICF	Informed Consent
IP	Investigational Product
ITT	Intention to Treat

Gan & Lee Pharmaceuticals USA

PRA HEALTH SCIENCES

Sponsor: Gan & Lee Pharmaceuticals USA Corporation
Protocol no: GL-GLAT1-3001

Statistical Analysis Plan
Version Date: 27-May-2021

SS	Safety Analysis Set
T4	Free Thyroxine
TEAE	Treatment-Emergent Adverse Event
TFLs	Tables, Figures, and Listings
TOST	Two One-Sided Tests
TSH	Thyroid-Stimulating Hormone
ULN	Upper Limit of Normal
WBC	White Blood Cell

Sponsor: Gan & Lee Pharmaceuticals USA Corporation
Protocol no: GL-GLAT1-3001

PRA HEALTH SCIENCES

Statistical Analysis Plan
Version Date: 27-May-2021

Metabolism and nutrition disorders	Hypercalcemia	Corrected serum calcium of $>\text{ULN}$ - 11.5 mg/dL; $>\text{ULN}$ - 2.9 mmol/L; Ionized calcium $>\text{ULN}$ - 1.5 mmol/L	Corrected serum calcium of $>\text{ULN}$ - 11.5 mg/dL; $>\text{ULN}$ - 2.9 mmol/L; Ionized calcium $>\text{ULN}$ - 1.5 mmol/L	Corrected serum calcium of >12.5 - 13.5 mg/dL; >3.1 - 3.4 mmol/L; Ionized calcium >1.6 - 1.8 mmol/L; hospitalization indicated	Corrected serum calcium of >13.5 mg/dL; >3.4 mmol/L; Ionized calcium >1.8 mmol/L; life-threatening consequences
Metabolism and nutrition disorders	Hypocalcemia	Corrected serum calcium of $<\text{LLN}$ - 8.0 mg/dL; $<\text{LLN}$ - 2.0 mmol/L; Ionized calcium $<\text{LLN}$ - 1.0 mmol/L	Corrected serum calcium of <8.0 - 7.0 mg/dL; <2.0 - 1.75 mmol/L; Ionized calcium <1.0 - 0.9 mmol/L; symptomatic	Corrected serum calcium of <7.0 - 6.0 mg/dL; <1.75 - 1.5 mmol/L; Ionized calcium <0.9 - 0.8 mmol/L; hospitalization indicated	Corrected serum calcium of <6.0 mg/dL; <1.5 mmol/L; Ionized calcium <0.8 mmol/L; life-threatening consequences
Investigations	Creatinine increased	>1 - $1.5 \times$ baseline; $>\text{ULN}$ - $1.5 \times \text{ULN}$	>1.5 - $3.0 \times$ baseline; $>\text{ULN}$ - $3.0 \times \text{ULN}$	$>3.0 \times$ baseline; >3.0 - $6.0 \times \text{ULN}$	$>6.0 \times \text{ULN}$
Metabolism and nutrition disorders	Hyperglycemia	Fasting glucose value $>\text{ULN}$ - 160 mg/dL; Fasting glucose value $>\text{ULN}$ - 8.9 mmol/L	Fasting glucose value >160 - 250 mg/dL; Fasting glucose value >8.9 - 13.9 mmol/L	Fasting glucose value >250 - 500 mg/dL; >13.9 - 27.8 mmol/L; hospitalization indicated	>500 mg/dL; >27.8 mmol/L; life-threatening consequences
Metabolism and nutrition disorders	Hypoglycemia	Fasting glucose value $<\text{LLN}$ - 55 mg/dL; $<\text{LLN}$ - 3.0 mmol/L	<55 - 40 mg/dL; <3.0 - 2.2 mmol/L	<40 - 30 mg/dL; <2.2 - 1.7 mmol/L	<30 mg/dL; <1.7 mmol/L; life-threatening consequences; seizures
Metabolism and nutrition disorders	Hyperkalemia	Blood potassium value $>\text{ULN}$ - 5.5 mmol/L	>5.5 - 6.0 mmol/L	>6.0 - 7.0 mmol/L; hospitalization indicated	>7.0 mmol/L; life-threatening consequences
Metabolism and nutrition disorders	Hypokalemia	Blood potassium value $<\text{LLN}$ - 3.0 mmol/L	$<\text{LLN}$ - 3.0 mmol/L; symptomatic; intervention indicated	<3.0 - 2.5 mmol/L; hospitalization indicated	<2.5 mmol/L; life-threatening consequences
Metabolism and nutrition disorders	Hyponatremia	Plasma sodium $<\text{LLN}$ - 130 mmol/L	-	<130 - 120 mmol/L	<120 mmol/L; life-threatening consequences
Metabolism and nutrition disorders	Hypernatremia	Plasma sodium $>\text{ULN}$ - 150 mmol/L	>150 - 155 mmol/L	>155 - 160 mmol/L; hospitalization indicated	>160 mmol/L; life-threatening consequences

Gan & Lee Pharmaceuticals USA

PRA HEALTH SCIENCES

Sponsor: Gan & Lee Pharmaceuticals USA Corporation
Protocol no: GL-GLAT1-3001

Statistical Analysis Plan
Version Date: 27-May-2021

